Moderation Hypothesis 1: Baseline levels of catastrophizing will be associated with response to the CT intervention, such that among those participants assigned to the CT intervention, individuals higher in catastrophizing scores at baseline will be more likely to evidence pre- to post-treatment decreases in pain interference than those individuals scoring lower in catastrophizing at baseline. This positive association between baseline catastrophizing and response to CT treatment will be stronger than the association between baseline catastrophizing and response to either the MM or AS treatments (although we would anticipate that all three associations will be positive, because MM and AS treatments are hypothesized to have an indirect effect on catastrophizing, consistent with the Shared Mechanisms Model).

Moderation Hypothesis 2: Baseline activity levels will be negatively associated with response to the AS intervention, such that among those participants assigned to the AS intervention, individuals lower in activity levels will be more likely to evidence pre- to post-treatment decreases in pain interference than those individuals evidencing higher activity levels at baseline. This negative association between baseline activity level and response to AS treatment will be stronger than the association between baseline activity level and response to either CT or MM treatments (although we would anticipate that all three associations will be negative, because CT and MM treatments will have an indirect effect on activity level, consistent with the Shared Mechanisms Model).

Moderation Hypothesis 3: Baseline levels of non-judgment will be associated with response to the MM intervention, such that those participants assigned to the MM intervention who score higher in baseline non-judgmental awareness will be more likely to evidence pre- to post-treatment decreases in pain interference than those individuals evidencing lower levels of non-judgment at baseline. This positive association between the baseline level of non-judgmental awareness and response to MM treatment will be stronger than the association between baseline non-judgmental awareness and response to either AS or CT treatments (although we would anticipate that all three associations will be

positive, because AS and CT treatments will have an indirect effect on non-judgmental awareness, consistent with the Shared Mechanisms Model).

A2d. Additional Exploratory Tests

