Exploratory Moderators	Cognitive Abilities Treatment Credibility COVID-19	PROMIS Cognitive Function Abilities (6 items ext. only) Treatment Credibility & Expectancies items (5 items EMA only) Investigator-developed items on COVID-19's effects (6 items ext. & 1 item Qualitative Interview)
Covariate	Primary Problem (LBP primary or secondary)	Baseline Self-Report
Optional Assessments	Responses to Pain Future Self Values-Consistent Goals	Positive & Negative Response to Pain Scales (85 items) Future Self Questionnaire (FSQ) (16 items) Valued Living Scale (VLS) (8 items)
Qualitative Outcomes	Experiences in group & program feedback	15-30" of investigator-developed qualitative items

Table 4. Study Assessment Schedule

Measures	EMA	Baseline	Pre-Treatment	During Treatment	Post-Treatment	3-Month	6-Month
Demographic Information		X					
Pain and Treatment History		X					
Start Back Tool		X					
Pain Medication Questionnaire (PMQ)		X					
Roland Morris Disability Questionnaire SF (RMDQ)		X					
PROMIS Pain Interference	X		X		X	X	X
Pain Appraisal Scale (PAS)	X		X		X	X	X
2-item Catastrophizing Scale from the Coping Strategy Questionnaire (CSQ)			X		X	X	X
Pain-Related Cognitive Process Questionnaire (PCPQ) Non-Judgment Scale	X		X		X	X	X
Godin Leisure-Time Exercise Questionnaire	X		X		X	X	X
Hours Spent Sitting w/o Exercising	X						
Pain Intensity NRS	X	X	X		X	X	X
Positive and Negative Affect Schedule (PANAS)	X		X		X	X	X
PROMIS-29 Sleep Disturbance			X		X	X	X
PROMIS-29 Physical Function			X		X	X	X
PROMIS-29 Depression			X		X	X	X
PROMIS-29 Anxiety			X		X	X	X
PTSD Checklist (PCL-C)			X		X	X	X
Medication & Cannabis Use			X		X	X	X
UW Pain-Related Self-Efficacy Scale	X		X		X	X	X
Participant Engagement				X ^a			
Working Alliance Inventory (WAI)	X ^b						
Group Climate Questionnaire (GCQ-S)	X ^b						
Duration and Times Practicing Skills	X				X	X	X
Sleep/Wake Times	X						
Health Care Utilization			X		X	X	X
Pleasant Events Schedule SF			X		X	X	X
Behavioral Activation for Depression Scale (BADS)			X		X	X	X
Global Quality of Life			X		X	X	X
Employment Status	X	X			X	X	X
Weight	X	X			X	X	X
Mindful Awareness and Attention Scale (MAAS)			X		X	X	X
Pain Resilience Scale			X		X	X	X
Pain-Related Cognitive Process Questionnaire (PCPQ) – Full			X		X	X	X
Control, Harm, Disability, and Medication Scales from the Survey of Pain Attitudes (SOPA)			X		X	X	X
PROMIS Cognitive Function Abilities			X		X	X	X
COVID-19 Impact Questions			X		X	X	X
Treatment Credibility and Expectancies	X ^c						

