At the end of the study when it comes time to conduct data analysis, study investigators (including those unblinded to intervention, such as both co-PIs) may need access to the data, in order to conduct specific analyses. Since (1) no investigators would be able to link any individual participant whose name was heard in fidelity recordings to any study data, and (2) any data investigators (blinded or unblinded) have access to at this point in the project would be locked, it is thus possible for unblinded investigators to also partake in data analysis.

Any staff member listed above may, with discretion from the co-PIs, participate in the actual writing/editing portion of any manuscript(s) that result from this study. During the data collection

phase of the study, blinded staff will not analyze or report data. Once the data is locked, all staff members, unblinded or blinded, may assist with analyzing or reporting data as needed.

D6s. Statistical Analyses

Structural equation modeling (SEM) will be used to evaluate the extent to which early treatment changes in catastrophizing, activity level, and non-judgment predict subsequent late treatment changes in pain interference, and the extent to which these associations are shared across the three treatments, or if some are unique to a subset of the treatments (Aim 1). We will also use SEM to examine the mechanisms of maintenance of gains from post-treatment to follow-up, to address the secondary study aim. Relevant covariates will be tested for and appropriately controlled for (when indicated) across all models. The Hochberg and Benjamini procedure will be used to control for alpha inflation in all analyses. This alpha control procedure involves putting the significance levels of the planned primary analyses in ascending order, and matching them to the actual significance levels obtained with the analyses, also placed in ascending order.

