Specifically, we propose to evaluate mechanism effects of the three treatments using a 3-wave SEM approach⁹⁸⁻¹⁰². To address Aim 1, we will calculate coefficients representing the linear change in each outcome and mechanism variable during the first two weeks of treatment (early treatment) and second two weeks of treatment (late treatment). To accomplish this, the slope of the regression line for predicting scores from the time variable will be obtained, where the Time variable consists of equally spaced fractions from 0 to 1 for each epoch (i.e., early treatment and late treatment represent two time epochs). While the majority of participants will provide many data points during these time periods, we only need two (representing just 2/24 EMA assessments, or 8% of requested data) ratings in each time period to be able to calculate the slopes for the planned analyses (see below for how any data deemed to be missing at random will be handled using this slope method). To address Aim 1, the time epochs/slopes will be operationalized/calculated as described below:

1. Pre-treatment scores: Slope calculated from EMA ratings/ActiGraph data from all available baseline data (i.e., from days 1-14, see Figure 2).
2. Early-treatment scores: Slope calculated from EMA ratings/ActiGraph data from the first day following the baseline period to mid-treatment (i.e., days 15-28, see Figure 2).
3. Late-treatment scores: Slope calculated from EMA ratings/ActiGraph data from the first day following the mid-treatment mark until the last day of the treatment period (i.e., days 29-42, see Figure 2).

To address the secondary Aim 2, we will calculate slopes from EMA and ActiGraph data across two time periods to compute scores for early and late post-treatment change for the primary outcome (pain interference) and the three mechanism variables (catastrophizing, non-judgment, and activity level), as operationalized below:

1. Early post-treatment scores: Slope calculated from EMA ratings/ActiGraph data from the first day following treatment until 2-weeks following treatment (i.e., from days 43-56, see Figure 2).
2. Late post-treatment scores: Slope calculated from EMA ratings/ActiGraph data from the first day following mid-post-treatment follow-up epoch until the end of the 4-week post-treatment period (i.e., days 57-70, see Figure 2).

Figure 2. EMA data collection and data time points used in analyses

[figure not shown]
[figure not shown]

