Figure 4. SEM model evaluating the "Limit" component of the LAE model

In the model depicted in Figure 4, while significant change in outcome from pre- to post-treatment is expected, it is anticipated that the effect of treatment condition on outcome will be non-significant (i.e., we anticipate that all three treatments will be associated with similar pre- to post-treatment improvements in pain interference, as reflected by non-significant a_1 and a_2 coefficients). However, the LAE model predicts that the post-treatment pain interference score, when controlling for pre-treatment pain interference, will be significantly associated with baseline levels of pain catastrophizing (i.e., path b in the model). We will also test the b coefficient for significance across each of the three moderating variables. The extent to which the effect of the baseline moderator variable predicting outcome varies as a function of treatment will then be evaluated (i.e., the c_1 and c_2 coefficients in Figure 4). These two pathways from condition to path b in the model, when combined and examined as a single parameter, if significant, will indicate the presence of a Treatment \times Moderator interaction. In the event that this interaction effect is identified, post hoc tests will be conducted separately for each treatment condition. Continuing with the example shown in Figure 4, if baseline catastrophizing is found to be negatively associated with subsequent outcome, and this effect is stronger in CT than in MM and AS, then this will be interpreted as lending support for the predictions made with respect to the “Limit” component of the LAE model.

Additional Exploratory Analyses

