Because it is likely that we will encounter at least some missing data despite procedural efforts by research staff to minimize its occurrence, we have attempted to further address missing data in a number of ways via our data analysis approach. First, we will examine potential patterns of missing data that represent confounds contributing to biased slopes. So, for each participant, analyses to identify potential patterns in missing data will be conducted to determine if they are “ignorable” (see Schafer & Grahem, 2002)¹⁰⁷. If >5% of the participants do not provide adequate data, the sample will be divided into two groups (missing data, no missing data) and fully observed variables will be examined to determine if they significantly predict missingness on the affected outcome. This test will be done on a variable-by-variable basis. If this analysis is non-significant, the missingness will be considered “observed at random” and the procedures described below for calculation of slope coefficients in the instance of missing data will be used, without necessitating the use of multiple imputation procedures. However, if no data is available to calculate slope via the below methods, in Mplus, the missing data (slopes and estimated end values from slopes) are treated automatically (by default) by estimating the full model from available data using full information maximum likelihood (FIML). The Mplus robust maximum likelihood (MLR) estimator using FIML permits missing completely at random (MCAR) and missing at random (MAR), and MLR uses SEs that are corrected for non-normality and also uses a corrected chi-square fit statistic. If data missingness is not ignorable, Heckman’s selectivity models of pattern-mixture models with multiple imputation will be used to model the “missingness” for each participant before calculation of slopes from the daily EMA and ActiGraph data.

There are several ways to treat data that are deemed to be missing at random (from the daily EMA and ActiGraph data) using the slope method. For example, consider the six cases below (from real data). The dependent variable was measured at five equally spaced intervals within the epoch. Within the current study, there are additionally two observations per day, and we propose to calculate the slopes from morning and evening observations, and to average those slopes.

Cases	0	0.25	0.5	0.75	1	Slope	Difference
1	12	14	15	15	10	-1.2	-2
2	12	10	11	10	7	-4	-5
3	23	19	13	13	12	-11.2	-11

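### The Aim 1 text prespecifies a baseline slope but no baseline level, so path b is open to confounding by where participants start

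*Combined protocol and SAP*

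**What the plan says.** D6s builds the Aim 1 model from three epochs. For each one, "the slope of the regression line for predicting scores from the time variable will be obtained", with time scaled from 0 to 1. The baseline term is "Pre-treatment scores: Slope calculated from EMA ratings/ActiGraph data from all available baseline data" (days 1-14). The early-treatment and late-treatment scores are slopes over days 15-28 and 29-42.

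Steps 1 and 2 of D6s then name two treatment dummies, the early mechanism slope and late change in interference. A significant b is read as support for the mechanism, and the a and b results together decide between the Shared and Specific Mechanisms Models. No baseline level of the mechanism or of interference is named in these steps.

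Three other places bear on the point:

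- **Covariates.** D6s says "Relevant covariates will be tested for and appropriately controlled for (when indicated) across all models". D6p describes covariates as variables to be controlled for if needed. The one row that Table 3 labels as a covariate is whether low back pain is the primary or a secondary problem.
- **Missing data.** D6t says "the missing data (slopes and estimated end values from slopes) are treated automatically (by default" in Mplus. It does not say what the end values are or where they enter the model.
- **Exploratory analyses.** Baseline level is modelled explicitly only here. The prediction is that "the post-treatment pain interference score, when controlling for pre-treatment pain interference, will be significantly associated with baseline levels of pain catastrophizing". Moderation Hypothesis 1 in A2c expects that, in the cognitive therapy arm, "individuals higher in catastrophizing scores at baseline will be more likely to evidence pre- to post-treatment decreases in pain interference". Hypotheses 2 and 3 make parallel statements for activity and non-judgment.

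**The concern.** Both ends of path b are measured after randomisation. Randomisation makes the arms comparable. It does not make people with a large early change in catastrophizing comparable with people with a small one. The covariate-adaptive allocation in D6k, which uses interference category, likewise balances arms and leaves b unprotected.

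If a person's starting level is related both to how fast the mechanism moves in the first two weeks and to how fast interference moves in the last two, b absorbs that shared dependence. The only baseline term the text defines is a slope, which says almost nothing about level. Three of the six planned primary tests are tests of b, so the exposure sits in the primary inference.

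**Working it through.** **The plan's own figures.** The documents give no figure on this point. Table 5 gives 109/129/140 for the mediation tests. Taking the smallest n with power(a) x power(b) of at least 0.80, two-sided, returns 111/131/142 by Fisher z and 107/126/137 by noncentral t. The interaction rows (93/98/102) reproduce exactly with 2 numerator df. Table 5 is not affected by this point.

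**Does the baseline slope stand in for level?** The slope is sum[(t - tbar)x] / sum[(t - tbar)^2] and the level is the mean of x. For a stationary series of 28 points (14 days x 2), the simulated correlation between the two was 0.000, 0.006 and 0.002 at lag-1 autocorrelations of 0, 0.5 and 0.9. Adjusting for the slope does not adjust for level.

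**Size of the spurious b.** Inputs are N = 240 (D6u), true b = 0, and an assumed correlation r of baseline level with each of the two slopes. The spurious correlation is r x r. The two-sided rejection rate is

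1 - Phi(z - d) + Phi(-z - d), where d = atanh(r x r) x sqrt(240 - 3).

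For r = .3: d = atanh(.09) x 15.39 = 1.39. At alpha .05 (z = 1.96) the rate is 1 - Phi(0.57) + Phi(-3.35) = 28%.

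A simulation with 3,000 trials per setting adjusted for both baseline slopes and two arm dummies but not for level. Table 5's strictest alpha is taken as .05/6 = .0083.

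| r with each slope | spurious r | alpha .05: formula | alpha .05: simulated | alpha .0083: formula | alpha .0083: simulated |
|---|---|---|---|---|---|
| .1 | .01 | 5.3% | 5.6% | 0.9% | 1.2% |
| .2 | .04 | 9.4% | 9.5% | 2.2% | 2.0% |
| .3 | .09 | 28.5% | 28.1% | 10.6% | 10.3% |
| .4 | .16 | 70.0% | 68.6% | 43.9% | 42.8% |

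The headline rates are rounded from these columns. If baseline slope and level correlate .3, the simulated rates at alpha .05 fall only to 5.0%, 8.0%, 21% and 58%.

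**After adding level.** The mean spurious b is 0.00, and rejection is 4.8% to 5.6% at alpha .05 for every r from .1 to .5.

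**Power kept.** For a true partial r of .30, Phi(atanh(.30) x 15.39 - z) is about .99 at alpha .017 and about .98 at alpha .0083.

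**The case against.** The strongest reply is that the text does not define the whole model. Step 2 sends the reader to Figure 3, which could not be seen. D6s has a general covariate clause, and D6t refers to end values that may be a level term. This stands. A reader might infer that baseline level never enters the model, but the documents do not show that. They show that it is not prespecified in the text. A clause applied when indicated leaves the choice until the data are in hand, and an undefined term does not settle it.

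A reader might also infer that the plan's own hypotheses make baseline level a common cause of both ends of b. They do not. A2c is exploratory and links level to pre- to post-treatment change in interference. It does not link level to early mechanism change, nor to the late slope in particular: someone who improves early and then plateaus fits Moderation Hypothesis 1 with a flat late slope. It follows that the documents do not establish an inflated b for catastrophizing and activity, or a masked b for non-judgment.

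Regression to the mean is a weak source here, because the windows do not overlap. In simulated stationary series with autocorrelation up to 0.7, baseline mean correlated 0.00 to -0.05 with the early slope and about 0.00 to 0.01 with the late slope. At 0.9 the values were -0.10 to -0.18 and about -0.01. Correlations near .3 would need treatment response to differ by starting level, which is plausible but not quantified in the documents.

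Two limits on size also stand. The plan's step-wise alpha control puts the actual rate between the .05 and .0083 columns. If Figure 3 conditions on early interference change, part of the confounding path may already be blocked. Were the bias to run against a true r of .30, then .30 - .09 = .21 still has about 91% power at alpha .05 and 74% at .0083.

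**Conclusion.** The point holds as a gap in prespecification. The Aim 1 text uses a baseline slope, names no baseline level, and reads b as evidence of mechanism. It is therefore right to say that b is open to confounding by baseline level. To say that b is confounded would go too far, since that needs two correlations the documents do not give and one link, from level to early mechanism change, that is a plausible inference and not a stated hypothesis.

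The effect is negligible at .1/.1 and material from about .3/.3, which is the size D6u calls medium. These figures assume no true effect, N = 240, equal correlations at both ends and no blocking by other terms in Figure 3. Severity: should-fix, because the exposed tests are primary and the remedy costs almost nothing.

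**What to change.** In each Aim 1 SEM, prespecify two covariates of both the early mechanism slope and the late interference slope: each person's days 1-14 mean of pain interference and of that model's mechanism. Keep the baseline slope if it is wanted. State in D6s that these covariates are always included, outside the clause on covariates tested for need. Define the end values mentioned in D6t and say whether they enter the model. If Figure 3 already contains baseline means, say so in the text.

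Take the levels from baseline monitoring. The Pre-Treatment assessment cannot supply an activity-count level, because it is completed before ActiGraph monitoring starts (D6g, D6j). Its catastrophizing and non-judgment scales also differ in length from the diary versions (Table 3: 5 items against 3, and 6 against 2). D6k allows randomisation from six days after monitoring starts, so some of days 1-14 can follow allocation; a Week 1 mean would serve as a sensitivity analysis.

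The cost is SAP wording and two covariates from data already collected, with negligible loss of power at N = 240.

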Figure 3 below represents the initial model we plan to test for the catastrophizing mechanism variable, providing that it evidences at least a small effect for change for at least one treatment condition during the first two weeks of treatment. However, the model will be simplified (by removing treatment condition as a predictor, and the paths associated with treatment condition) if non-significant treatment effects are found. Up to two additional SEM models will also be tested, with non-judgment and activity level as the foci. Below we describe the specific steps planned to address the study aims and test the primary study hypotheses.

Figure 3. Initial model testing the mechanism role of pain catastrophizing during treatment

Step 1. Ensure at least small time effects (slope) in the early mechanism variables for at least one of the treatment conditions (a requirement for that variable to be considered as a possible mechanism).

- (1) We will perform an initial one-way Analysis of Variance (ANOVA) comparing the pre- to mid-treatment mechanism slopes between the three treatment conditions, separately for each of the three mechanism variables, with a goal of identifying the effect (i.e., Eta squared, η^2) associated with any between group differences in early changes in mechanism variable. If this effect size is < 0.01 , this would indicate a less than small between-group difference in the amount of early treatment change for that mechanism;

this would be interpreted to mean that all three treatment conditions had a similar effect on early treatment change in the mechanism variable.

- (2) In the event that a less than small between condition effect is found, we would then examine the pre- to mid-treatment time effect of this mechanism collapsed across groups to see if this mechanism changes from pre- to mid-treatment (i.e., early treatment). If this effect size (η^2) associated with this time effect collapsed across groups for any mechanism variable is less than 0.01 (representing a small time effect) then there would be evidence that the variable in question is unlikely to act as a mechanism, because at least some change over time early in treatment for that variable, on average, is needed for it to serve as a mechanism.

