- (3) If less than small effects emerge for both the between-group effects on the early mechanism slope *and* for the time effect (i.e., average slope), this would be interpreted to indicate a lack of early change (in any treatment condition) on the mechanism variable. In this instance, that mechanism variable would not be tested in a subsequent SEM. If *either* of the effect sizes are equal to or larger than 0.01 (indicating a small or larger time effect, on average) or a small or large Group X Time effect emerges (indicating at least a small group effect on early change in mechanism), then we will proceed to Step 2 for that mechanism variable.

Step 2. Test the model presented in Figure 3 for any mechanism variable that met the Step 1 conditions described above.

- (4) First paths a_1 and a_2 will be tested. The a_1 and a_2 coefficients represent the strength of the predictive relationships from the two dummy IVs¹ to early treatment slope in catastrophizing (i.e., to evaluate the impact of treatment condition on early treatment changes in catastrophizing). Together, these tell us if treatment condition had a direct effect on the early treatment slope in the mechanism variables. If both of these coefficients are non-significant (consistent with the Shared Mechanisms Model) they will be eliminated from the final SEM. If either or both of these pathways are statistically significant, this will be interpreted to mean that there is a between-treatment condition difference in early change in the mechanism variable being evaluated, and these effects will be retained in the model.
- (5) In the case of at least one statistically significant a coefficient, we will perform planned post-hoc ANOVA models for each of the three treatment groups to understand these differences and to determine if the findings are consistent with the Specific Mechanisms Model. For example, if catastrophizing is uniquely targeted by CT, we would anticipate a significant treatment condition effect (in either or both of the two a coefficients) on early catastrophizing slope, with post hoc tests indicating larger pre- to mid-treatment decreases in catastrophizing for the CT condition than the MM or AS interventions. However, the full test of the Specific Mechanisms Model also takes into account the b path, described below.

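### Neither a small sample eta squared (Step 1) nor non-significant a paths (Step 2) can show that the three treatments act similarly, and passing Step 1 does not establish early change

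*Combined protocol and SAP*

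**What the plan says.** All of this is in the combined protocol and SAP, section D6s (Statistical Analyses).

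- **Purpose of Step 1.** It is there to "Ensure at least small time effects (slope) in the early mechanism variables for at least one of the treatment conditions", as a condition for treating the variable as a possible mechanism.
- **Step 1, item (1).** A one-way ANOVA is run, "comparing the pre- to mid-treatment mechanism slopes between the three treatment conditions". "If this effect size is < 0.01 , this would indicate a less than small between-group difference", and "this would be interpreted to mean that all three treatment conditions had a similar effect on early treatment change in the mechanism variable".
- **Step 1, items (2) and (3).** The arms are pooled and the same .01 cut-off is applied "for the time effect (i.e., average slope"). A variable is dropped only when both values fall short. It goes on to Step 2 if either "of the effect sizes are equal to or larger than 0.01 (indicating a small or larger time effect, on average") or the between-arm effect is at least small.
- **Step 2, item (4).** If both a paths are non-significant, this counts as consistent with the Shared Mechanisms Model and the paths are removed.
- **Paragraph after item (6).** A significant b path with non-significant a paths supports the Shared Mechanisms Model, and the plan explains this as the treatments having a like impact on the mechanism.

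Neither step gives a confidence interval, an equivalence margin or an error rate for the similarity conclusion. Hypothesis 1b (A2a) expects arm effects that are both small and non-significant. Step 2 checks only the second of these.

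**The concern.** Similarity of the three arms is one of the two main answers the trial can give. A sample effect size below a cut-off, or a p value above one, says only that no difference was shown. It does not bound how large the difference could be. Followed exactly, the plan can report that the treatments share a mechanism when the data are compatible with differences several times its own definition of small.

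Step 1 is also presented as making sure that the variable moved early in treatment. If noise alone often exceeds .01, it does not do that. On the shared-mechanism route no later step tests mean change: item (5) adds further ANOVAs only when an a path is significant.

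**Working it through.** **Inputs.** Cut-off .01 for both effect sizes (D6s, Step 1). N = 240, 80 per arm (Précis; Table 5). 300 are to be randomised (A2), with 20% dropout (D5).

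**The plan's own figures.** The plan states no error rate or margin for either rule, so there is none to reproduce. Its sample-size figures do reproduce. Enrolment is 240/(1 − 0.20) = 300. The interaction rows of Table 5 (f² = .15, 2 df, λ = f²N, power .80) give 93, 98 and 102 exactly. The mediation rows (joint significance, r = .30) give 111, 131 and 142 against the stated 109, 129 and 140. None of these rows concerns similarity.

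**1. The cut-off as a test.** F = (.01/2)/(.99/237) = 1.197 on (2, 237) df, p = .304. With no arm difference, the expected sample eta squared is already 2/239 = .0084.

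**2. What an observed value at the cut-off leaves open.** Find λ such that P(F′(2, 237; λ) ≤ 1.197) equals .05 or .025. The upper limit is λ/(λ + 240).

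- Two-sided 90%: λ = 8.73, so 8.73/248.73 = .035. f = √(.035/.965) = .19, largest pairwise d about 0.40 to 0.47.
- Two-sided 95%: λ = 10.80, so 10.80/250.80 = .043. f = .21, largest pairwise d about 0.45 to 0.52.
- At N = 300 the limits are .032 and .039.

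The .01 cut-off therefore acts as an unstated margin of about .035.

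**3. How often a real difference is labelled similar.** With λ = 240η²/(1 − η²):

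| True η² | λ | Step 1: P(F′ < 1.197) | Step 2: P(F′ < 3.03) |
|---|---|---|---|
| .01 | 2.42 | 36% | 74% |
| .02 | 4.90 | 17% | 51% |
| .04 | 10.0 | 3% | 19% |

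The last column treats the two a paths as one 2-df test at .05 without covariates (critical F = 3.03). This is my simplification of item (4). A stricter alpha under the plan's multiplicity procedure would raise these figures.

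**4. How often a null variable passes Step 1.** Take no mean change and no arm difference, with the time effect as a one-sample test of the mean slope.

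- Between arms: p = .304.
- Time: F(1, 239) = .01 × 239/.99 = 2.414, p = .122.
- Either: 1 − (.696 × .878) = .389. Simulation of 100,000 trials gave 38.6%.
- N = 300: 1 − (.775 × .917) = .289. N = 192: .489.

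**5. Is a margin rule workable at N = 240?** Declare similarity if the 90% upper limit is below margin m, that is, if F is below the 5th percentile of F′(2, 237; 240m/(1 − m)). With no true difference:

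| Margin m | F must be below | Similarity shown |
|---|---|---|
| .02 | 0.447 | 36% |
| .04 | 1.50 | 77% |
| .059 | 2.86 | 94% |

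**The case against.** The strongest reply is that Step 1 is a deliberately lenient pre-screen. Passing it supports no claim. Every variable that passes still faces tests of a1, a2 and b under the plan's multiplicity control, and Table 5 already allows for all six tests. This stands: the gate does not inflate the a and b tests. A reader might take 39% as a false-positive rate for the trial's mechanism findings, but the documents do not support that. The figure is the rate at which a null variable enters testing. What remains is one route: zero average change, a chance pass, and a b path that is significant because individual slopes predict outcome.

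The second reply is that the similarity sentence in Step 1 does not itself produce the Shared Mechanisms conclusion. This also stands. If both values are below .01 the variable is dropped. If only the between-arm value is below, a1 and a2 are tested afresh. An F below 1.197 also limits any contrast in that ANOVA to |t| of about √(2 × 1.197) = 1.55, so Step 2 would ordinarily find nothing either. This moves the main weight of the problem to Step 2, where non-significance is read as like impact. Deleting the Step 1 sentence alone would leave that conclusion unchanged.

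Third, a reader might infer that a near-medium arm difference is likely whenever the plan says similar. It is not: a true .04 falls under the cut-off only 3% of the time. The commoner error is to call a truly small difference similar.

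**Conclusion.** The point holds in this form. The plan turns a small estimate (Step 1) and a non-significant test (Step 2) into a statement of similarity, and neither can carry it. At N = 240 the data behind a Step 1 reading of similar are compatible with an eta squared of up to .035 (90%) or .043 (95%). The plan's own small effect earns that label 36% of the time. If .04 were an acceptable margin, an observed value under .01 would in fact meet it. The fault is that no margin is stated or justified.

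Step 1 does not ensure early change: a null variable passes about 39% of the time. That figure assumes a usable slope for all 240, no arm difference as well as no mean change, and a time effect taken from the average slope as item (3) words it. It is 29% at N = 300. If the time effect's denominator included between-person variance, it would fall towards the between-arm rate of 30%. Clustering by treatment group was not modelled and would raise the between-arm pass rate. A reader might go further and say that at least one of three null mechanisms passes 77% of the time. That needs the three to be independent, which the documents do not say.

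The a and b tests remain valid. What is affected is what may be concluded when the a paths are not significant.

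**What to change.** In section D6s:

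1. Delete the sentence in Step 1, item (1), that reads a value below .01 as similarity.
2. In Step 2, item (4), and in the paragraph after item (6), claim similarity, and hence a shared mechanism, only if the upper end of the two-sided 90% interval for the between-arm effect on the early slope lies below a margin fixed and justified before unblinded analysis. Otherwise report the result as inconclusive.
3. Report the pooled mean early slope with its confidence interval for each mechanism, so that a shared-mechanism claim can be read against evidence that the variable changed.
4. Describe Step 1 as a lenient screen and not as proof of change.

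This needs no new data, visits or participants. The cost is that some results now called shared will become inconclusive. With no true difference, similarity would be shown about 36% of the time at a margin of .02, 77% at .04 and 94% at .059, so the margin has to be chosen with that in view.

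Replacing eta squared by bias-corrected omega squared in the screen is not required. At the same .01 cut-off it would lower the null pass rate from 39% to 17%, but raise the chance of missing a true between-arm effect of .01, on the between-arm part, from 36% to 60%. That is a trade-off for the investigators.
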